11.1 Frequency of Data and Safety Monitoring

The Sponsor will be informed of serious adverse events as soon as they occur and will notify Merck within 24 hours of notification. The frequency of data review for this study differs according to the type of data and can be summarized in the following table.

Data Type	Frequency of Review	Reviewer
Stopping Rules (Treatment Response)	Biweekly Quarterly	Conference Call among sites PI, Sponsor, DSMB
Subject accrual (including compliance with protocol enrollment criteria)	Quarterly	, Sponsor, DSMB
Status of all enrolled subjects, as of date of reporting	Quarterly	Sponsor, DSMB
Adherence data regarding visits and intervention	Quarterly	Sponsor, DSMB
AEs and rates (including out-of-range lab values)	Quarterly	Sponsor, DSMB
SAEs	Per occurrence	PI, Merck

11.2 Contents of Data and Safety Monitoring Report

The content of the data and safety monitoring report will include study status, participant descriptive information, safety information and measures of study quality. See DSMR document for table templates.

11.3 Safety Stopping Rules

Sponsor and DBMB will meet quarterly to review the patient data for safety as related to the stopping rules as defined in this section.

If a patient experiences grade 3 or higher toxicities (excluding grade 3/4 hematologic toxicity) deemed at least possibly related to the study drug (and not clearly disease related), or if grade 2 laboratory (excluding grade 2 hematologic toxicity) or clinical toxicities deemed at least possibly related to the study drug (and not clearly disease related) do not resolve within 3 weeks in spite of treatment, we will stop study drug administration.

If, among the MF-CP (primary cohort) patients, 3 or more of the first 5, 4 or more of the first 10, 6 or more of the first 15, or 7 or more of the first 24 patients stop study drug within the first 3 cycles due to toxicity as defined above in the previous paragraph, we will stop

Product: MK-3475

Protocol/Amendment No.:

enrolling patients to the primary cohort. The probability of stopping early if the true toxicity rate is 20%, 30%, 40% or 45% is 0.18, 0.51, 0.81, 0.91, respectively.

If, among the MPN-AP/BP (exploratory cohort) patients, 2 or more of the first 5 or 3 or more of the first 10 patients, stop study drug within the first 3 cycles [due to toxicity as defined above in the previous paragraph](#), we will stop enrolling patients to the exploratory cohort. The probability of stopping early if the true toxicity rate is 20%, 30%, 40% or 50% is 0.26, 0.48, 0.66, 0.81, respectively.

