2.1 Trial Design

This is a multicenter, open-label, Phase 2 study to assess the efficacy, safety and tolerability of pembrolizumab in patients with chronic phase myelofibrosis (MF-CP) defined as either patients with primary myelofibrosis (PMF), post essential thrombocythemia (post-ET) or polycythemia vera (post-PV) myelofibrosis (primary cohort). We propose a Simon-two stage design for this study. We will test pembrolizumab at the FDA approved dose (in head and neck cancer) of 200mg dose administered via intravenous infusion over 30 minutes given every 3 weeks. Nine patients will be enrolled in the first stage of the Simon-two stage design, and 15 in the second stage. A treatment cycle is 3 weeks and the core study period is 6 cycles. Response assessment by established consensus criteria will be used to assess response after 6 cycles in order to determine if the trial will progress to the second stage and for the purpose of determining the primary endpoint. In addition, we will allow a maximum of ten patients with accelerated or blast phase disease (MPN-AP/BP) who are refractory or intolerant to conventional therapies such as decitabine, and in which hematopoietic stem cell transplant is not a therapeutic option (exploratory cohort), to enroll in the study as a separate exploratory cohort. These patients can be enrolled during stage 1 or 2 and they will be analyzed separately from the primary cohort population. The study will therefore enroll a maximum of 34 patients.

The study will enroll at 3 centers (Mount Sinai, NY; Montefiore, NY; Massachusetts General Hospital, MA).

Exploratory biomarkers will be obtained from enrolled patients at baseline, cycle 3 and cycle 7 and at 1 year of therapy. Patients that obtain at least a clinical improvement after 6 cycles of therapy can continue receiving pembrolizumab until evidence of disease progression, unacceptable toxicity, and patient or physician decision for a maximum of 2 years.

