The choice of the 200 mg Q3W as an appropriate dose for the switch to fixed dosing is based on simulations performed using the population PK model of pembrolizumab showing that the fixed dose of 200 mg every 3 weeks will provide exposures that 1) are optimally consistent with those obtained with the 2 mg/kg dose every 3 weeks, 2) will maintain individual patient exposures in the exposure range established in melanoma as associated with maximal efficacy response and 3) will maintain individual patients exposure in the exposure range established in melanoma that are well tolerated and safe.

A fixed dose regimen will simplify the dosing regimen to be more convenient for physicians and to reduce potential for dosing errors. A fixed dosing scheme will also reduce complexity in the logistical chain at treatment facilities and reduce wastage.

4.2.3 Study Design and Statistical Methods:

This is an open-label phase II trial to assess the efficacy, safety and tolerability of pembrolizumab in patients with PMF, post-PV MF, and post-ET MF. We propose a Simon

Two-Stage design for this study; the first 9 MF patients will be enrolled to confirm a signal of activity and safety of pembrolizumab at the FDA approved dose (in head and neck cancer) of 200mg administered via intravenous infusion over 30 minutes given every 3 weeks for six cycles.

In stage 1, if at least one response (out of 9 subjects in the primary cohort) is observed after six cycles of treatment at week 18, 15 additional patients will be accrued in the second stage (total of 24 evaluable patients in the primary cohort). If however, fewer than 3 of 24 patients respond to therapy, pembrolizumab will be deemed not worthy of any further investigation in this patient population. If response is seen in greater than or equal to 3 of 24 patients, pembrolizumab will be considered to have activity in this patient population and will be recommended for further study. For this study we define inactivity as a response rate of 5%, and activity as a response rate of 25%, which is comparable to that seen with ruxolitinib in a mixed population. The probability of erroneously concluding that the drug has activity if the true but unknown response rate is 5% is 0.10. The power to detect a response rate of 25% with this design is 0.90.

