5.2.1.2 Dose Modification

Adverse events (both non-serious and serious) associated with pembrolizumab exposure may represent an immunologic etiology. These adverse events may occur shortly after the first dose or several months after the last dose of treatment. Pembrolizumab must be withheld for drug-related toxicities and severe or life-threatening AEs as per Table 3 below. See Section 5.6.1 and Events of Clinical Interest Guidance Document for supportive care guidelines,

including use of corticosteroids. Although leukopenia, anemia, and thrombocytopenia are expected as a natural consequence of the disease being treated and will be present at baseline for the majority of enrolled subjects, grade 4 treatment emergent hematologic toxicity will require drug treatment interruption regardless of attribution and can be re-started once the hematologic toxicity has resolved to baseline or at least grade 3. Treatment emergent grade 3/4 anemia and thrombocytopenia will be managed with red blood cell and platelet transfusional support as pre treating investigators discretion.

Table 3. Dose Modification Guidelines for Drug-Related Adverse Events

Toxicity	Hold Treatment For Grade	Timing for Restarting Treatment	Discontinue Subject
Diarrhea/Colitis	2-3	Toxicity resolves to Grade 0-1.	Toxicity does not resolve within 3 weeks of last dose or inability to reduce corticosteroid to 10 mg or less of prednisone or equivalent per day within 12 weeks.
	4	Permanently discontinue	Permanently discontinue
AST, ALT, or Increased Bilirubin	2	Toxicity resolves to Grade 0-1	Toxicity does not resolve within 3 weeks of last dose.
	3-4	Permanently discontinue (see exception below) ¹	Permanently discontinue
Type 1 diabetes mellitus (if new onset) or Hyperglycemia	T1DM or 3-4	Hold pembrolizumab for new onset Type 1 diabetes mellitus or Grade 3-4 hyperglycemia associated with evidence of beta cell failure.	Resume pembrolizumab when patients are clinically and metabolically stable.
Hypophysitis	2	Toxicity resolves to Grade 0-1	Toxicity does not resolve within 3 weeks of last dose or inability to reduce corticosteroid to 10 mg or less of prednisone or equivalent per day within 12 weeks.
	3-4	Permanently discontinue	Permanently discontinue

Toxicity	Hold Treatment For Grade	Timing for Restarting Treatment	Discontinue Subject

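### The Section 11.3 enrolment-halting rule counts patients who stop drug, but Table 3 lets some patients with a qualifying toxicity restart or continue, so two counts are possible; as a minor point, Sections 5.8 and 7.2.3.1 give different SAE windows

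*Combined protocol and SAP*

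**What the plan says.** **Halting rule.** Section 11.3 sets the patient-level condition: "If a patient experiences grade 3 or higher toxicities (excluding grade 3/4 hematologic toxicity) deemed at least possibly related to the study drug". The same sentence adds non-hematologic grade 2 toxicity that has not resolved within 3 weeks despite treatment. In either case study drug stops, and no exception is listed. The next two paragraphs halt enrolment when enough "patients stop study drug within the first 3 cycles due to toxicity as defined above in the previous paragraph". The boundaries are 3 of 5, 4 of 10, 6 of 15 and 7 of 24 in the primary cohort, and 2 of 5 and 3 of 10 in the exploratory cohort. The operating characteristics are given per toxicity rate, for the exploratory cohort as "The probability of stopping early if the true toxicity rate is 20%, 30%, 40% or 50% is 0.26, 0.48, 0.66, 0.81, respectively".

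**Drug management.** Table 3 (Section 5.2.1.2) treats three categories differently:
- Diarrhea/colitis, grade 2-3: hold, then restart once "Toxicity resolves to Grade 0-1". Only grade 4 is an immediate permanent stop.
- Diabetes/hyperglycemia: "Hold pembrolizumab for new onset Type 1 diabetes mellitus or Grade 3-4 hyperglycemia associated with evidence of beta cell failure", then "Resume pembrolizumab when patients are clinically and metabolically stable".
- Hypothyroidism, grade 2-4: pembrolizumab may go on while the thyroid disorder is treated.

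The Table 3 note makes discontinuation permanent for a grade 3 event that recurs and for any life-threatening event. Section 5.8 takes its criterion for unacceptable adverse experiences from 5.2.1.2, not from 11.3.

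**SAE window.** Section 5.8 gives 90 days of SAE collection after end of treatment and cites 7.2.3.1 as the source. Section 7.2.3.1 requires all SAEs only until 30 days after treatment or the start of new anti-cancer therapy, whichever is earlier. After that it requires only SAEs judged related.

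**The concern.** The halting rule is a counting rule, so its numerator has to be the same whoever applies it. A patient with a first grade 3 colitis in cycle 2 meets the 11.3 condition. Under Table 3 the site may hold the drug and restart it. Nothing says whether that patient has stopped study drug for the purpose of the count. The sponsor and DSMB review the rule quarterly, and two careful readers could put different totals before them. The lower total makes halting less likely than a rule indexed by the toxicity rate implies.

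The SAE mismatch is smaller. A site working from 7.2.3.1 could stop reporting unrelated SAEs at day 30 while 5.8 tells it that collection runs to day 90.

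**Working it through.** **1. How far the conflict extends.**

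| Event meeting the 11.3 condition | 11.3 | Table 3 |
|---|---|---|
| Diarrhea/colitis, first grade 3 | stop | hold, restart allowed |
| New type 1 diabetes, or grade 3-4 hyperglycemia with beta cell failure | stop | hold, resume when stable |
| Hypothyroidism, grade 3-4 or persistent grade 2 | stop | continue |
| Pneumonitis, nephritis, hypophysitis, hyperthyroidism, infusion reaction, other; grade 3-4 | stop | permanent stop |
| AST, ALT or bilirubin, grade 3-4 | stop | permanent stop (exception for liver metastases) |
| Recurrent grade 3, or life-threatening | stop | permanent stop (note) |

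The disagreement is confined to the first three rows. Because the note removes life-threatening events, it consists mainly of first grade 3 events plus persistent grade 2 hypothyroidism. If a hold counts as a stop, only hypothyroidism can go uncounted. If it does not, all three rows can.

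**2. The plan's own probabilities.** For the exploratory 5-patient look, P(X ≥ 2) = 1 − (1−p)^5 − 5p(1−p)^4:
- p = 0.20: 1 − 0.3277 − 0.4096 = 0.263
- p = 0.30: 1 − 0.1681 − 0.3602 = 0.472
- p = 0.40: 0.663
- p = 0.50: 0.813

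The printed values are 0.26, 0.48, 0.66 and 0.81, which agree to within 0.01. They are first-look figures per toxicity rate.

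The printed primary values (0.18, 0.51, 0.81, 0.91 at 20, 30, 40, 45%) do not reproduce. An exact binomial recursion over the four written looks gives 0.25, 0.66, 0.92 and 0.97. Looks at 5, 10 and 15 alone give 0.15, 0.42, 0.71 and 0.82. A last look at 7 of 20 gives 0.175, 0.506, 0.813 and 0.906, which fits. That is a separate matter and nothing below depends on it.

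**3. Size without any assumption.** One uncounted patient is 1/2 of the exploratory 2-of-5 boundary and 1/3 of the primary 3-of-5 boundary.

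**4. Illustration with an assumed share.** The documents do not say what fraction of qualifying toxicity falls in the three categories. Let s be the uncounted share, so counted rate = true rate × (1 − s); for example 0.30 × 0.90 = 0.27. The primary columns give the chance of crossing at the looks at 5, 10 or 15; the exploratory columns use the look at 5. The looks at 24 and 10 are left out because each cohort is then full.

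| s (assumed) | Primary, true 20% | Primary, true 30% | Exploratory, true 20% | Exploratory, true 30% |
|---|---|---|---|---|
| 0% | 0.15 | 0.42 | 0.26 | 0.47 |
| 5% | 0.13 | 0.37 | 0.24 | 0.44 |
| 10% | 0.11 | 0.33 | 0.22 | 0.41 |
| 20% | 0.08 | 0.25 | 0.18 | 0.35 |
| 33% | 0.05 | 0.15 | 0.14 | 0.26 |

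The baseline depends on how the looks are read. If enrolment halts as soon as a boundary count is reached, the chance of halting before the cohort is full at a true 30% and s = 0 is 0.62 (primary, by patient 23) and 0.61 (exploratory, by patient 9).

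**5. SAE window.** 90 − 30 = 60 days (days 31 to 90) on which 5.8 and 7.2.3.1 disagree, for unrelated SAEs only. The gap opens sooner if new anti-cancer therapy starts before day 30. Section 5.8.1 schedules weekly contacts over those 60 days, but only for patients who stop after CR.

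**The case against.** The best reply is that 11.3 is self-contained. Its first paragraph says drug stops for every qualifying toxicity, and the count refers back to that definition. Inside 11.3, then, toxicity and stopping are the same event. This is right, and it disposes of one tempting inference: that the printed probabilities use the wrong index because they refer to a toxicity rate while the rule counts discontinuations. The index instead supports counting by event. What stands is that no text gives 11.3 precedence for dosing, and 5.8 sends sites to Table 3.

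A reader might also infer that the halting rule is seriously weakened or that patients are unprotected. The documents do not support that. The affected categories are few, only cycles 1 to 3 matter, and no incidence is given, so nothing supports the larger shares in the table. There are other protections: quarterly DSMB review of AEs and rates (11.1), termination for adverse-reaction incidence or severity (5.10), and advance approval of rechallenge after a serious, possibly drug-caused event (Table 10). None of them settles which count the rule uses.

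On SAEs, one might say that collecting and reporting are different activities. But 5.8 names 7.2.3.1 as its source, so the distinction does not reconcile the two. Nor does the SAP lack a window. Section 8.2.3.1 limits AE summary tables to events that start or worsen on treatment, and 8.2.3 ends that period 30 days after the last dose; later events are still listed and flagged. Related SAEs remain reportable at any time.

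**Conclusion.** The concern holds in a narrow form. Sections 11.3 and 5.2.1.2 give contradictory instructions for three toxicity categories, and because 5.8 relies on Table 3, a compliant site can produce a lower halting count than 11.3 intends. This is a contradiction between stated rules, worth correcting because the early boundaries are 2 and 3 patients.

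The firm statement of size is one patient as half or a third of a first-look boundary. The halting probabilities are illustrative: they rest on assumed uncounted shares, on independent patients with a constant rate, and on the chosen looks. The primary baseline of 0.15 and 0.42 at 20% and 30% also does not match the printed 0.18 and 0.51. If the share is small, the effect is small. The primary efficacy analysis is not affected.

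The SAE mismatch is real and minor: unrelated SAEs over 60 days.

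**What to change.** **Section 11.3.** Count every patient in either cohort who has an 11.3-qualifying toxicity in the first 3 cycles, whether drug was held, continued or stopped. The clinical team may expressly exempt hormone-replaced hypothyroidism. State that Table 3 governs drug management, or list its exceptions in 11.3.

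*Cost:* wording, and a somewhat higher chance of halting enrolment. In the illustration at a true 20% rate and a 10% share, counting by event moves the primary cohort from 0.11 to 0.15 and the exploratory 5-patient look from 0.22 to 0.26. Exempting hypothyroidism would shrink that increase.

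**Section 7.2.3.1.** Set 90 days for all SAEs and keep the any-time rule for related ones. If SAEs on days 31 to 90 are to be tabulated, also amend the sentence in SAP Section 8.2.3.1 that confines AE summary tables to the on-treatment period; otherwise the two will conflict.

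*Cost:* reporting of unrelated SAEs over 60 more days. Extending the 5.8.1 weekly contacts to all patients is optional.

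### The primary-cohort stopping probabilities in Section 11.3 do not follow from the stated toxicity boundaries, and stopping early is not defined

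*Combined protocol and SAP*

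**What the plan says.** Section 11.3 of the combined protocol and SAP counts patients who stop study drug for toxicity within the first three cycles. For the primary cohort the earlier limits are 3 of 5, 4 of 10 and 6 of 15 patients, and the last limit reads "or 7 or more of the first 24 patients stop study drug within the first 3 cycles due to toxicity". Reaching a limit closes enrolment to that cohort. The rule's performance is then given as: "The probability of stopping early if the true toxicity rate is 20%, 30%, 40% or 45% is 0.18, 0.51, 0.81, 0.91, respectively".

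The exploratory cohort has limits of 2 of the first 5 and 3 of the first 10, with this statement: "The probability of stopping early if the true toxicity rate is 20%, 30%, 40% or 50% is 0.26, 0.48, 0.66, 0.81, respectively".

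On cohort size, Section 4.2.3 says "15 additional patients will be accrued in the second stage (total of 24 evaluable patients in the primary cohort"), and Section 2.1 says "we will allow a maximum of ten patients with accelerated or blast phase disease (MPN-AP/BP"). The last look in each cohort therefore falls at full enrolment. On timing, Section 11.3 says "Sponsor and DBMB will meet quarterly to review the patient data for safety as related to the stopping rules". The plan does not say which looks count as stopping early, or how the probabilities were calculated.

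**The concern.** The stopping probabilities of a rule like this follow from its boundaries by exact calculation, so a reader should be able to reproduce them. The primary-cohort figures cannot be reproduced. The missing definition matters because a limit first reached at patient 24 of 24 has almost no enrolment left to stop.

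These figures are how a DSMB or IRB judges whether the rule protects patients without closing the cohort needlessly. If all looks count, the plan understates both the risk of a false stop at 20% toxicity and the chance of detecting 40 to 45% toxicity. If only looks before full enrolment count, it overstates detection, which is the less safe direction.

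**Working it through.** **Inputs.** Primary limits 3/5, 4/10, 6/15, 7/24 and exploratory limits 2/5, 3/10 (Section 11.3). Maximum cohort sizes 24 (Section 4.2.3) and 10 (Section 2.1). Toxicity rates p as printed. Patients are taken as independent with constant p, and outcomes as complete at each look.

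**Formula.** Let X_n be the number of toxicity stops among the first n patients. With all looks counted,

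P(stop) = 1 − P(X_5 ≤ 2, X_10 ≤ 3, X_15 ≤ 5, X_24 ≤ 6).

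This is evaluated by carrying the surviving paths from look to look. First step at p = 0.20: P(X_5 ≥ 3) = 10(0.2³)(0.8²) + 5(0.2⁴)(0.8) + 0.2⁵ = 0.0512 + 0.0064 + 0.0003 = 0.0579.

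**Primary cohort, cumulative probability of having stopped:**

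| True rate | by look 5 | by look 10 | by look 15 | by look 24 | printed |
|---|---|---|---|---|---|
| 20% | 0.0579 | 0.1377 | 0.1505 | 0.2471 | 0.18 |
| 30% | 0.1631 | 0.3726 | 0.4200 | 0.6582 | 0.51 |
| 40% | 0.3174 | 0.6356 | 0.7091 | 0.9185 | 0.81 |
| 45% | 0.4069 | 0.7478 | 0.8203 | 0.9695 | 0.91 |

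A simulation of 1,000,000 runs agrees for all four looks (0.247, 0.658, 0.918, 0.970).

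**Readings compared with the printed 0.18, 0.51, 0.81, 0.91:**

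| Reading | 20% | 30% | 40% | 45% |
|---|---|---|---|---|
| All four looks | 0.247 | 0.658 | 0.919 | 0.970 |
| Looks at 5, 10, 15 only | 0.15 | 0.420 | 0.709 | 0.820 |
| Any crossing up to patient 23 | 0.225 | 0.619 | 0.897 | 0.958 |
| 7 of 24 as a single look | 0.189 | 0.611 | 0.904 | 0.964 |
| Strictly more than each limit, all looks | 0.104 | 0.457 | 0.819 | 0.919 |

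No row fits all four printed values. Letting the stage-one futility stop compete (approximate) gives about 0.18, 0.48, 0.74, 0.83 at a 5% response rate and 0.24, 0.64, 0.90, 0.95 at 25%. Neither fits.

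**A rule that does fit.** Moving only the last look from 24 to 20 patients (7 of 20) gives 0.1754, 0.5060, 0.8131, 0.9059, which rounds to all four printed values. The plan gives no look at 20. A carry-over from a different cohort size is therefore an inference.

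**Exploratory cohort.** First look at 30%: P(X_5 ≥ 2) = 1 − 0.7⁵ − 5(0.3)(0.7⁴) = 1 − 0.1681 − 0.3602 = 0.472.

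| Reading | 20% | 30% | 40% | 50% |
|---|---|---|---|---|
| First look only (2 of 5) | 0.263 | 0.472 | 0.663 | 0.813 |
| Both looks | 0.389 | 0.669 | 0.860 | 0.955 |
| Printed | 0.26 | 0.48 | 0.66 | 0.81 |

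The printed figures match the first look alone, apart from 0.48 for 0.47. That convention leaves out the look at full enrolment. Applied to the primary cohort it gives the 5, 10, 15 row, not the printed values.

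**The case against.** The strongest reply is that the readings above assume outcomes are known at once, while the rule has a three-cycle (9-week) window and quarterly review. Suppose the 24 primary patients accrue at about one a month over the 24-month enrolment period in Section 1.0, and only stops before the last patient enrols count. Simulating the limits as written then gives:

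| Assumed accrual and event timing | 20% | 30% | 40% | 45% |
|---|---|---|---|---|
| Poisson, events spread over 9 weeks | 0.186 | 0.526 | 0.826 | 0.914 |
| Poisson, events known at week 9 | 0.175 | 0.504 | 0.797 | 0.895 |
| Even, events spread over 9 weeks | 0.182 | 0.522 | 0.826 | 0.915 |
| Even, events known at week 9 | 0.162 | 0.475 | 0.781 | 0.883 |

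The first three rows lie within 0.02 of every printed value. So it would be too strong to say the figures can arise only from a last look at 20. However, the plan states no accrual or event-timing model. The same approach gives about 0.30 to 0.34 for the exploratory cohort at 20%, against the printed 0.26. It does not make both sentences true.

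A second reply is that the all-looks figures count a stop that is not early. That has force: the look at 24 alone adds 0.097, 0.238, 0.209 and 0.149, and apart from replaced patients little enrolment then remains to be stopped. This argues for a definition. It does not rescue the printed figures, because leaving that look out gives values below them.

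Finally, the practical effect is limited, because the DSMB acts on counts. That is accepted and reflected in the weight given to the point.

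**Conclusion.** The concern holds. The printed primary-cohort probabilities do not follow from the stated limits at the stated looks, and none of the definitions tested makes both cohorts' sentences correct.

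- **All looks counted:** the printed figures are too low by 0.07, 0.15, 0.11 and 0.06. The false-stop risk at 20% toxicity is 0.25, not 0.18.
- **Only looks at 5, 10 and 15 counted:** they are too high by 0.03, 0.09, 0.10 and 0.09. Detection at 40% and 45% is 0.71 and 0.82, not 0.81 and 0.91.

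The direction of the error cannot be settled until the sponsor says what stopping early means. The results assume independent patients, a constant toxicity rate and complete outcomes at each look. Quarterly review with a 9-week window would lower the figure for crossings up to patient 23 by an amount the plan does not fix. The point should be corrected, but it does not affect the sample size, any analysis or the usability of the limits.

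**What to change.** In Section 11.3, reconcile the limits with the probabilities and define stopping early once for both cohorts. The definition should say which looks count, whether a crossing between looks counts, and whether the look at full enrolment counts. If the figures came from an accrual and delay model, state that model. Then restate both sets for the limits the sponsor confirms. For the limits as written:

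| Definition | Primary (20/30/40/45%) | Exploratory (20/30/40/50%) |
|---|---|---|
| All looks | 0.25, 0.66, 0.92, 0.97 | 0.39, 0.67, 0.86, 0.96 |
| Fixed looks before the cohort is full | 0.15, 0.42, 0.71, 0.82 | 0.26, 0.47, 0.66, 0.81 |

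No change to any limit is proposed. The cost is one definition and one sentence per cohort, with no extra patients or procedures. The sponsor would have to state less favourable figures in one respect or the other: a higher false-stop risk on the first definition, or lower detection in the primary cohort on the second.
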